# **Group versus Individual Delivered Cognitive Behavioral Therapy for Complicated Grief Reactions: A Randomized Non-inferiority Trial.**

## **Statistical analysis plan for the non-inferiority study**

**Version 1.0. July 2024**

This statistical analysis plan describes the methods used to analyze the primary and secondary outcomes from the CBTgrief trial pre-registered at [www.clinicaltrials.gov](https://www.clinicaltrials.gov) (identifier: NCT04694807). This analysis plan was constructed during data collection before data access. Analyses of the hypotheses about moderators and mediators will be registered and reported separately and will not be further mentioned in this registration.

### **Research objectives and hypotheses for non-inferiority study**

**Background and rationale:** See information at [www.clinicaltrials.gov](https://www.clinicaltrials.gov) (identifier: NCT04694807).

#### **Aims of the study:**

- Evaluate the relative efficacy of an individually delivered versus group-based CBTgrief.

#### **Primary hypothesis:**

- Group-based CBTgrief will show non-inferiority in reducing symptoms of PGD (PG-13) compared to individually delivered CBTgrief at six months follow-up.

#### **Secondary hypotheses:**

- Group-based CBTgrief will show non-inferiority in reducing symptoms of PGD (PG-13) compared to individually delivered CBTgrief at post-intervention.
- Group-based CBTgrief will show non-inferiority in reducing symptoms of A) posttraumatic stress (PCL-5), B) depression (CESD-10), and C) anxiety (GAD-7) compared to individually delivered CBTgrief at 1) post-intervention and 2) six-month follow-up.
- Group-based CBTgrief will show greater reductions in loneliness (TILS) than individual CBTgrief at 1) post-intervention and 2) six-month follow-up.
- Group-based CBTgrief will show higher levels of received social support (CSS) than individual CBTgrief at 1) post-intervention and 2) six months follow-up.

Moreover, we will examine differences in terms of well-being (WHO-5), quality of life (SF-12), and grief-related functional impairment (SDS) between the two delivery formats.

## **Study methods**

### **Design**

Non-inferiority design of group versus individually delivered CBTgrief. See more information at [www.clinicaltrials.gov](https://www.clinicaltrials.gov) (identifier: NCT04694807).

### **Randomization**

Block randomization with a 1:1 allocation ratio to individually delivered versus group-based CBTgrief conducted by an independent Danish National Center for Grief employee.

### **Sample size**

See information at [www.clinicaltrials.gov](http://www.clinicaltrials.gov) (identifier: NCT04694807).

### **Timing of outcome measures**

Baseline characteristics will be assessed at the time of inclusion (T1). Outcome measures will be assessed pre-treatment (T1), post-treatment (T2), 3 months follow-up (T3), and 6 months follow-up (T4).

The study also assessed outcomes at mid-treatment (i.e., after session 6), but this time point was included for investigating therapy processes and will be analyzed and reported separately in another research paper with another research question.

See information about measures at [www.clinicaltrials.gov](http://www.clinicaltrials.gov) (identifier: NCT04694807).

### **Statistical principles**

### **Data presentation**

The CONSORT reporting guidelines for non-inferiority and equivalence trials will be applied. Results for the non-inferiority hypotheses will be reported accordingly.

### **Adherence and protocol deviations**

Attrition rates will be reported for both groups (received individually delivered vs. group-based CBTgrief). We will make the following categories: 1) Non-starters (participants that were randomized but received no therapy sessions), 2) Completers (participants receiving 8 or more sessions of therapy), and 3) Dropouts (participants dropping out of the treatment will be divided into early dropouts (before session 6) and late dropouts (after session 6)).

Therapist fidelity and adherence to the manual will be assessed for individually delivered CBTgrief and group-based CBTgrief. Thirty percent of all completed individual and group therapies (i.e., completed more than 8 sessions of therapy) will be randomly chosen to be rated for fidelity and adherence to the manual. The presence of the core components of the manual will be assessed as well as the quality of the application of these components session-by-session. Two master psychology students will receive comprehensive training in the manual by KK in doing these. KK will analyze 20% of the selected individual and group therapies for interrater agreement. These will be chosen randomly.

### **The analysis population**

As recommended by the CONSORT guidelines for reporting noninferiority and equivalence randomized trials (Piaggio et al., 2012) we will do Intention-to-treat (ITT), but also per-protocol (PP) analyses as sensitivity analysis.

### **Trial population**

### **Eligibility**

See more information at [www.clinicaltrials.gov](http://www.clinicaltrials.gov) (identifier: NCT04694807)

### **Recruitment**

See information at [www.clinicaltrials.gov](http://www.clinicaltrials.gov) (identifier: NCT04694807).

[figure not shown]
Adjustments: Originally, recruitment was planned at two clinical sites (clinics in Odense and Copenhagen, DK). However, due to difficulties with recruitment at the clinical site in Odense, randomization for group versus individual CBTgrief was not possible at that site. A pilot study has reported data from the clinical site in Odense (<https://osf.io/qp67d>). In the present non-inferiority trial, we only focus on the data collected at the clinical site in Copenhagen, where randomization of group versus individually delivered CBTgrief was possible.

## Participant flow

Example of how the participant flow will be presented for the study according to CONSORT.

**Figure 1.**

Participant flow in the present study.

## Baseline characteristics

See the example below of what baseline characteristics will be reported.

**Table 1.**

Participant characteristics at baseline.

Characteristic	Total sample (n=)	Individual CBT (n=)	Group CBT (n=)
Age, mean (SD)			
Gender, n (%)			
Female			
Male			
Education a , n (%)			
Primary education			
Secondary education			
Source of income b , n (%)			
Salary			
Pension			
Out of employment			
Other			
Relationship to the deceased, n (%)			
Spouse/partner			
Parent			
Other			
Years together, mean (SD) c			
Illness prior to death, n (%)			
Yes			
No			
Cause of death, n (%) d			
Cancer			
Cardiovascular disease			
Dementia			
Suicide			
Accident			
COVID-19			
Other age-related illness			
Time since loss (months), mean (SD)			
Additional bereavement losses, mean (SD)			
Previous use of psychosocial support prior to intervention, n (%) e			
Symptom profiles f			
PGD g only			
PGD and PTSD h			
PGD and depression			
PGD and anxiety			
PGD and $\geq$ two syndromes			
PGD and $\geq$ three syndromes			

Notes. a) Education will be categorized as primary education (primary school, high school, vocational training) and secondary education (college, university); b) Source of income will be categorized as 1) salary for those holding a job, 2) pension for those on early voluntary retirement and those receiving self-financed or government-assisted pension, and 3) out of employment (including unemployment benefits, social security payments due to sickness, or government-sponsored support); c) Only relevant for partner

loss; d) cause of death will be reported by the participant; e) Psychosocial support includes contacts with a psychiatrist, psychologist, counseling (e.g., patient organizations), and social support groups; f) Syndromes will be assessed based on self-report measures with cut-off values on clinically relevant symptom levels. Thus, no psychiatric diagnoses will be given; g) Prolonged grief disorder; h) Posttraumatic stress disorder.

## Analyses

### Primary outcome

Symptoms of PGD. See details at [www.clinicaltrials.gov](https://www.clinicaltrials.gov) (identifier: NCT04694807).

### Secondary outcomes

Symptoms of depression, PTSD, and anxiety, functional impairment, loneliness, social support, quality of life, well-being, treatment satisfaction. See details at [www.clinicaltrials.gov](https://www.clinicaltrials.gov) (identifier: NCT04694807).

### Process variables

Process variables included: Experience of unrealness, negative loss-related cognitions, avoidance behaviors, therapeutic alliance, and therapeutic group processes. See details at [www.clinicaltrials.gov](https://www.clinicaltrials.gov) (identifier: NCT04694807). These will be reported in a separate paper about therapeutic processes and mechanisms of CBTgrief.

## Analysis methods

### Descriptive analyses

Baseline group differences will be explored with t-tests and  $\chi^2$ -tests.

### Inferential analyses

The analyses will be based on comparisons of group CBTgrief versus individually delivered CBTgrief.

#### Primary analysis

The primary analysis will examine whether group CBTgrief is non-inferior to individual CBTgrief.

The analyses for primary and secondary outcomes will consist of multilevel, mixed linear models (MLMs) including time (pre-intervention, post-intervention, 3-month follow-up, and 6-month follow-up), group (Group CBTgrief vs. Individual CBTgrief), and their interaction (Time x Group). Two-level MLMs will be used to test the Time x Group interaction effect taking into account that symptoms are measured at several time points (level 1) that are nested within individuals (level 2).

We will report between and within-group effect sizes (Cohen's  $d$ ) for both group and individual-delivered CBTgrief to assess change in symptoms over time in the respective treatment groups.

The rationale for the non-inferiority limit: The choice of the non-inferiority margin of 0.5 SD was based on a clinical judgment, considering that the minimal important difference has yet not been established on PG-13. 0.5 SD corresponds to the border between a mild and medium effect, which very often corresponds to the border for a clinically meaningful effect (Norman et al., 2003) – also for stressor-related disorders such as PTSD (0.5-0.8 SD; Stefanovics et al., 2018). Moreover, a recent meta-analysis found that grief-focused CBTs delivered individually had a medium pooled effect on PGD symptoms with the lower bound of the 95% confidence interval (CI) of 0.49 (Hedge's  $g$  = 0.67, 95% CI: 0.49-0.85; Komischke-Konnerup et al., 2024). Importantly, RCTs investigating individual-delivered grief-focused CBTs that specifically included similar interventions and theoretical backgrounds as CBTgrief have found large effects on PGD symptoms compared to active and passive control groups (Cohen's  $d$  = 0.90 – 1.34; Boelen et al., 2007; Reitsma et al.,

2023). Thus, based on previous research, individually delivered CBTgrief was expected to be highly effective in reducing PGD symptoms. Group CBTgrief may have potential advantages over individually delivered CBTgrief for an older bereaved population. In older bereaved individuals, loneliness and less social support are common, and a group format can offer a safe space and community for sharing one's grief experiences with and receiving support from other bereaved individuals. Furthermore, group-based treatment may be associated with more practical and financial advantages such as reduced costs and fewer specialized therapists needed to treat a larger group of individuals. Based on this rationale, a non-inferiority margin of 0.5 was chosen. This means that a mild effect up to the border of medium effect in favor of individual CBTgrief will be acceptable for determining the non-inferiority of group CBTgrief.

The true difference between group and individual delivered CBTgrief is assumed to be 0.0 and the one-sided significance level (alpha) of the test is 0.025 (Flight & Julius, 2016). A one-sided 97.5% CI interval approach will be used to test non-inferiority between group and individual CBTgrief. The 97.5% CI will be calculated for between-group differences at 6-month follow-up and post-intervention (Cohen's  $d$ ). The non-inferiority of group CBTgrief will be accepted if the lower bound of the 97.5% CI lies within the non-inferiority margin (Cohen's  $d = -0.5$ ). If the non-inferiority of group CBTgrief is accepted, we will further assess the potential superiority of group CBTgrief by close testing procedure (i.e., if the lower bound of the 97.5% CI lies above 0) (Flight & Julius, 2016).

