### **Secondary analysis**

The secondary analyses will follow the same principle as the primary analysis for PTSD, depression, anxiety, functional impairment, quality of life, treatment satisfaction, and well-being – testing for non-inferiority of group vs. individual CBTgrief.

For loneliness and social support, we will test the superiority of the group-based CBTgrief with MLMs using a two-sided alpha = 0.5 for significant differences, following our hypotheses.

Reliable changes in symptoms of PGD, PTSD, anxiety, and depression were computed by the Reliable Change Index (RCI; Jacobson & Truax, 1991) on the completer sample for both group and individually delivered CBT format and from pre- to post-intervention and 6-month follow-up.

Additionally, we will calculate the percentages of A) recovered participants (scoring above cut-offs before but below after treatment), B) unchanged participants (no change in terms of cut-offs before and after treatment), and C) deteriorated participants (scoring below cut-offs before treatment but above after treatment).

Based on the two-step criterion, individuals will be classified as 1) recovered (met both Cutoff A and RCI), 2) improved (met RCI but not Cutoff A), 3) unchanged (met none of the criteria), or 4) deteriorated (met RCI but symptom scores increased). See the procedure used by e.g., (Papa et al., 2013); Reitsma et al. (2023); (Treml et al., 2021).

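### Loneliness and social support: superiority is hypothesised at post-intervention and six months, but the only model test named is the Time x Group interaction, and no visit-level decision rule is given

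*SAP*

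**What the plan says.** Under Secondary hypotheses, the SAP makes two directional statements, each for two visits. The one on loneliness is: "Group-based CBTgrief will show greater reductions in loneliness (TILS) than individual CBTgrief at 1) post-intervention and 2) six-month follow-up". The one on social support is: "Group-based CBTgrief will show higher levels of received social support (CSS) than individual CBTgrief at 1) post-intervention and 2) six months follow-up".

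Under Primary analysis, one type of model serves all outcomes: "The analyses for primary and secondary outcomes will consist of multilevel, mixed linear models (MLMs"). Its time term is listed visit by visit, "including time (pre-intervention, post-intervention, 3-month follow-up, and 6-month follow-up"), and group and the interaction are the other terms. The test named for it is: "Two-level MLMs will be used to test the Time x Group interaction effect". The same section then gives a decision rule for non-inferiority: a one-sided 97.5% confidence bound on the group difference at six months and post-intervention, with a follow-on step for superiority.

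Under Secondary analysis, that principle is extended to seven listed outcomes. Loneliness and social support are not among them. Their own sentence begins: "For loneliness and social support, we will test the superiority of the group-based CBTgrief with MLMs". It then sets the level and refers back to the hypotheses: "using a two-sided alpha = 0.5 for significant differences, following our hypotheses".

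Table 2 has rows for each visit, including for these two outcomes. Its between-group columns (F, p, and Cohen's d with a 95% CI) stand under a Time x Group Interaction heading.

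**The concern.** These are the only two outcomes that the SAP tests directly for superiority. Each hypothesis names a direction and two visits. The interaction has no direction and covers all visits, so it answers a different question: whether the two arms' profiles differ anywhere over the four assessments. A difference confined to 3 months can make it significant when neither hypothesised difference exists.

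The social support hypothesis also concerns levels, whereas an interaction concerns differences in change.

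With no rule stated, the analyst could choose after seeing the data among the F test, a T2 difference, a T4 difference, a change score or a level. The point has some weight because the rationale for the non-inferiority margin cites loneliness and lack of social support as reasons to value the group format. The primary non-inferiority conclusion is not affected.

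**Working it through.** **No figure to reproduce.** The SAP refers to the registry for sample size and states no power for these tests.

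**Inputs from the SAP.** Four visits; two arms, 1:1; hypotheses at T2 and T4 only.

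**Assumptions.**
- Level: two-sided 5%. The printed level is 0.5, which is a separate point.
- Outcome: SD 1, complete data, compound symmetry with correlation r = 0.3, 0.5 or 0.7.
- Arm size: n = 40, 63 or 85. The last two follow from the SAP's margin of 0.5 SD, true difference of 0 and one-sided 0.025: 2(1.96 + 0.842)² / 0.5² = 62.8, so 63 (80% power); 2(1.96 + 1.282)² / 0.5² = 84.1, so 85 (90% power). 40 is a lower value for the range.

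**Step 1, degrees of freedom.** With time as a factor, (4 − 1)(2 − 1) = 3. The 5% critical value of chi-square on 3 df is 7.81.

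**Step 2, non-centrality.** Let d₁ to d₄ be the true group differences at T1 to T4. Under compound symmetry,

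λ = n / [2(1 − r)] × Σ(dₜ − mean d)².

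For 0.5 SD at 3 months only, d = (0, 0, 0.5, 0), the mean is 0.125 and the sum is 0.25 − 4 × 0.125² = 0.1875.

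At n = 63 and r = 0.5, λ = 63 × 0.1875 = 11.81, and the 3-df test is significant in 83% of trials.

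| n per arm | r = 0.3 | r = 0.5 | r = 0.7 |
|---|---|---|---|
| 40 | 47% | 62% | 86% |
| 63 | 68% | 83% | 97% |
| 85 | 82% | 93% | 99.6% |

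**Step 3, the same truth with a visit contrast.** The true differences at T2 and T4 are 0. A two-sided 95% interval excludes 0 in favour of group in 2.5% of trials, for each contrast, whatever n and r.

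**Step 4, power for a real benefit.** The change contrast at one visit has SE = √[4(1 − r)/n]. At n = 63 and r = 0.5 this is 0.178. For a 0.5 SD benefit, 0.5/0.178 = 2.81 and power is Φ(2.81 − 1.96) = 80%. For the same benefit sustained at T2, T3 and T4, the 3-df test has λ = 11.81 again and 83% power.

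**Step 5, if time were linear (1 df).** With scores −1.5, −0.5, 0.5 and 1.5, the 3-month-only case gives a slope difference of 0.5 × 0.5/5 = 0.05, with SE √[2(1 − r)/(5n)] = 0.056 at n = 63 and r = 0.5. The test is significant in 14% of trials (9% to 27% over the grid). A common slope does not isolate T2 or T4 either.

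**The case against.** The text leans towards the hypotheses. The sentence on these outcomes ends by referring back to them, and they fix both direction and visits. Table 2 has rows by visit and a Cohen's d with a 95% CI. If it is filled in by visit, much of what is needed is already in the reporting shell. This stands, and it narrows the gap to one thing: no test or decision rule is tied to those estimates.

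The SAP does not say that time is categorical. That also stands. The 3 df are inferred from the four named visits, and under linear time the 3-month-only problem is much smaller.

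A 0.5 SD difference at 3 months with exactly none at T2 and T4 is an extreme case. It shows what the test responds to and is not a forecast.

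A reader might infer two stronger points that the document does not support:

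- **That a significant F would be reported as superiority even if group did worse.** With group 0.5 SD worse at T2, T3 and T4, the 3-df test is significant in 83% of trials (n = 63, r = 0.5). This is only the power of a non-directional test. It misleads only if the sign of the estimates is ignored, and nothing in the SAP says that it would be.
- **That the interaction test loses power.** This depends on the correlation pattern. For a sustained 0.4 SD benefit with 64 per arm, the 3-df test and the six-month change contrast have 48% and 48% power at r = 0.3, 63% and 62% at 0.5, and 87% and 83% at 0.7. The contrast leads (54% against 48%) if correlations among follow-up visits (0.70 to 0.80) exceed those with baseline (0.40 to 0.50). The SAP gives no correlations.

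**Conclusion.** The concern holds as a mismatch between hypothesis and test, limited to loneliness and social support. The SAP names one model test, and it does not address superiority at T2 or T4. The rule that would address these visits is not extended to these two outcomes, and the visit-level estimates implied by Table 2 carry no decision rule.

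With time as a factor, a 0.5 SD difference at 3 months alone makes the interaction significant in about 47% to 99.6% of trials, against 2.5% for a false benefit at each T2 or T4 contrast. The range rests on the assumed arm sizes, compound symmetry, complete data and a 5% level. The mismatch itself does not depend on these figures. The case for change rests on answering the stated hypotheses, not on power. These are secondary outcomes, so the change is advisable but not critical to the trial's main conclusion.

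**What to change.** In Secondary analysis, state that loneliness and social support will each be tested by two pre-specified 1-df contrasts, group against individual, at T2 and at T4, taken from the planned mixed model with time as a four-level factor.

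- **Scale:** change from baseline for loneliness, as hypothesised. For social support, state whether level or change is compared.
- **Decision rule:** give a two-sided 95% CI, and claim superiority at a visit only if the interval excludes 0 in favour of group.
- **Multiplicity:** state how the four contrasts (two outcomes at two visits) are handled. Holm is one option.
- **Interaction F:** report it as descriptive.

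The cost is SAP wording; no new data and no new model are needed. The downside is that a difference confined to 3 months would not count as a hypothesis test and could only be described.

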### **Handling of missing data and blinding**

Item level: If less than 50% of items on a scale are missing and Cronbach alpha is above .7, missing items will be handled via multiple imputations. If more than 50% of items on a scale are missing, then it will result in a missing value at the scale level.

Scale level: If the entire scale (e.g., PCL-5 at 3-month follow-up) is not completed then it will be left empty.

Survey-level: We will not impute missing data on the survey level (i.e. if participants have not returned/completed an entire questionnaire).

Analyses level: MLMs handle missing data by using maximum likelihood estimation, assuming that data is missing at random or completely at random.

Treatment conditions (group vs. individual) will randomly be coded “1” or “2” in the data file and concealed until all non-inferiority analyses are done.

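### The primary mixed model leaves out the therapy group, so any positive within-group correlation makes the non-inferiority interval too narrow and pushes one-sided alpha above 0.025

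*SAP*

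**What the plan says.** The SAP, Primary analysis, specifies mixed linear models with time, treatment arm and their interaction. It defines two levels: "symptoms are measured at several time points (level 1) that are nested within individuals (level 2"). The only term called group is the fixed effect for treatment arm.

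The same section sets the decision rule: "A one-sided 97.5% CI interval approach will be used to test non-inferiority between group and individual CBTgrief", and "The non-inferiority of group CBTgrief will be accepted if the lower bound of the 97.5% CI lies within the non-inferiority margin", which is Cohen's d = -0.5. It adds that "the one-sided significance level (alpha) of the test is 0.025". If non-inferiority is shown, the same bound is compared with 0 to test superiority.

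Under Secondary analysis, "The secondary analyses will follow the same principle as the primary analysis". The Sensitivity analyses section varies only the analysis set: intention-to-treat, at least 8 sessions, or all 12 sessions. No section adds a random effect for therapy group or therapist, a cluster-robust variance, or a design effect.

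The rationale for the margin describes members of a therapy group sharing experiences and "receiving support from other bereaved individuals". The Process variables section lists group processes in therapy among the things measured.

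**The concern.** The two-level model treats all participants as independent once the repeated measures within a person are accounted for. That may hold between participants treated one to one. It is doubtful for people who attend the same sessions with the same fellow members, and the SAP presents mutual influence as a reason for preferring the group format. Because only one arm has therapy groups, the design is partially nested.

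If members of a therapy group have positively correlated outcomes after treatment, the mean of the group arm varies more than the model believes. In a superiority trial this would produce false claims of a difference. Here it produces false claims of non-inferiority, which is the trial's primary claim, and the follow-on superiority test inherits the fault. Running both intention-to-treat and per-protocol analyses gives no protection, since both use the same model. The mixed-model results for secondary outcomes are affected too. The reliable-change and cut-off percentages are not mixed-model results and lie outside this point.

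**Working it through.** **Inputs from the SAP:** one-sided alpha 0.025, margin d = -0.5, 1:1 allocation, primary time point 6 months, two-level model.

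**Assumptions, because the SAP gives no values:** therapy-group size m, intraclass correlation ρ, number per arm n, and equal total variance σ² in both arms.

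**Step 1, the plan's own figure.** With independent participants, a one-sided 97.5% interval has error 1 - 0.975 = 0.025. The stated alpha is reproduced.

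**Step 2, clustering in the group arm only, single endpoint.**

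- Variance of the arm difference under the planned model: 2σ²/n.
- Actual variance: (σ²/n) × {1 + [1 + (m - 1)ρ]}.
- Ratio: r = 1 + (m - 1)ρ/2.
- Correct SE divided by planned SE: √r. The planned SE is too small by 1 - 1/√r.
- Actual one-sided error: 1 - Φ(1.96/√r).

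| m | ρ | r | correct SE / planned SE | actual one-sided error |
|---|---|---|---|---|
| any | 0 | 1 | 1 | 2.5% |
| 6 | 0.01 | 1.025 | 1.012 | 2.6% |
| 10 | 0.01 | 1.045 | 1.022 | 2.8% |
| 4 | 0.05 | 1.075 | 1.037 | 2.9% |
| 6 | 0.05 | 1.125 | 1.061 | 3.2% |
| 8 | 0.05 | 1.175 | 1.084 | 3.5% |
| 8 | 0.10 | 1.350 | 1.162 | 4.6% |
| 10 | 0.15 | 1.675 | 1.294 | 6.5% |

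For example, with m = 8 and ρ = 0.10, r = 1 + 7 × 0.10/2 = 1.35, √r = 1.162, and 1.96/1.162 = 1.687, which leaves 4.6% in the tail. Over m = 6 to 10 and ρ = 0.05 to 0.15 the planned SE is 6% to 23% too small. The superiority step uses the same bound, so at a true difference of 0 its error is inflated by the same formula.

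**Step 3, the four-wave model.** The planned design was simulated with a random intercept per person, 60 to 64 per arm, within-person correlation 0.4 to 0.6, complete data, a therapy-group effect at the three post-baseline waves, and the true difference at the margin (20,000 trials per setting). With m = 6 to 10 and ρ = 0.05 to 0.15, the error for the 6-month difference was 3.1% to 6.6%. For the baseline-to-6-month Time x Group contrast it was 3.4% to 8.5%. With ρ = 0 all settings gave 2.3% to 2.8%. The closed form is therefore a fair guide for the 6-month difference.

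**Step 4, whether modelling the group repairs it.** A single-endpoint analysis of cluster means with arm-specific variance and Satterthwaite degrees of freedom gave an error of 2.4% to 2.8% over m = 4 to 10 and ρ = 0 to 0.15 (40,000 trials per setting).

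**The case against.** The omission and its direction are hard to dispute, but the size can be contested.

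- **The ICC is unknown.** Expecting mutual support makes a positive ICC plausible without saying how large it is. At ρ = 0.01 to 0.02 and m = 4 to 10 the error is only 2.6% to 3.0%, and the SAP supports that range no less than 0.05 to 0.15. This stands as a limit on the size. It does not rescue the model, which is exact only at ρ = 0, a value the SAP does nothing to justify.
- **The calculations assume full groups and a lasting effect.** The SAP expects non-starters, dropouts and unreturned questionnaires. If 75% of members were observed at 6 months, m = 8, ρ = 0.10 would give 4.0% instead of 4.6%, and m = 10, ρ = 0.15 would give 5.4% instead of 6.5%. A group influence that fades after treatment would also reduce the inflation at 6 months. Both points stand; they shrink the problem without removing it.
- **The 8.5% figure is not for the decision quantity.** It belongs to the change contrast under a random-intercept covariance that the SAP does not name. The interval is defined on between-arm differences at each time point, so 3.1% to 6.6% is the relevant simulated range.
- **There would be few therapy groups.** With about 64 per arm there might be 8 to 10. In a single-endpoint calculation the group variance was estimated at or below zero in 33% to 35% of trials at ρ = 0.05, and in 19% at m = 8, ρ = 0.10. Error in that simplified analysis nevertheless stayed at 2.2% to 2.5%. The full four-wave partially nested model was not itself simulated.
- **Therapists may also cluster outcomes, possibly in both arms.** This is true and is not quantified here. If individual-arm therapists treated several participants, treating each participant as a cluster of one is itself an approximation.

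**Conclusion.** The concern holds. The SAP fixes a hierarchy that stops at the person although one arm is treated in therapy groups, and no other provision covers the gap. For any positive within-group correlation the interval is too narrow and the one-sided error exceeds 0.025, in favour of non-inferiority. The size is conditional on group size and ICC, neither of which is in the document: negligible at ICC 0.01, and material from about 0.05 upward, where groups of 8 give 3.5% at ICC 0.05 and 4.6% at ICC 0.10. Because the stated alpha governs the trial's sole primary decision and the error is anti-conservative, this should be corrected before the non-inferiority analyses are run.

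**What to change.** In the SAP, Primary analysis, replace the two-level model with a partially nested mixed model:

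- Keep time within person. Add a therapy-group random effect for the group arm only, acting at the post-baseline time points, with each individual-arm participant as a cluster of one.
- Allow a separate residual variance in each arm and use Satterthwaite or Kenward-Roger degrees of freedom.
- Retain the therapy-group term whatever its p-value, report the ICC, and take both the non-inferiority and the superiority bound from this model. Use the same structure for the mixed-model secondary outcomes.
- The SAP counts as non-starters "participants that were randomized but received no therapy sessions". To preserve intention-to-treat, code group-arm participants who never joined a therapy group by their assigned group where one exists, and otherwise as singletons.
- State whether therapists treated several participants. If they did, add a sensitivity model with therapist identifier.

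The change needs SAP wording and one identifier variable, with no new outcome data. It costs power: in a single-endpoint illustration with 64 per arm, m = 8 and ICC 0.10, the chance of showing non-inferiority at a true difference of 0 falls from 77% to 63%. The higher figure is obtained only by using an understated SE. The identifier would also reveal the arm codes, which are to be masked "in the data file and concealed until all non-inferiority analyses are done", so the script should be fixed in advance or run by someone outside the masked team.

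### Does the cited lower confidence bound of 0.49 undermine the 0.5 SD non-inferiority margin?

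*SAP*

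**What the plan says.** The margin rationale is in the SAP under Primary analysis. It opens with its basis: "The choice of the non-inferiority margin of 0.5 SD was based on a clinical judgment", because no minimal important difference has been established for the PG-13. It then appeals to the half-SD convention, with a reference to stressor-related disorders. After that come two pieces of background on individual treatment. The first is a meta-analysis reporting "a medium pooled effect on PGD symptoms with the lower bound of the 95% confidence interval (CI) of 0.49", with g = 0.67 and a 95% CI of 0.49 to 0.85. The second is a set of trials of closely similar interventions, which found "large effects on PGD symptoms compared to active and passive control groups" (d = 0.90 to 1.34, no intervals given). From these the SAP infers that individual CBTgrief should work very well. It adds the possible social, practical and financial advantages of a group format and closes: "Based on this rationale, a non-inferiority margin of 0.5 was chosen".

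The next sentence spells out the consequence: "a mild effect up to the border of medium effect in favor of individual CBTgrief will be acceptable". The decision rule is "The non-inferiority of group CBTgrief will be accepted if the lower bound of the 97.5% CI lies within the non-inferiority margin", at Cohen's d = -0.5 and one-sided alpha 0.025. The primary hypothesis concerns group treatment "compared to individually delivered CBTgrief at six months follow-up".

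**The concern.** In a margin rationale, naming the lower confidence bound of the reference effect, and not only its estimate, suggests a fixed-margin argument. In that approach the lower bound is the effect that can safely be credited to the reference treatment, and the margin must be smaller than it, usually by enough to keep a stated share. Here the margin is slightly larger than the bound. Someone who sees 0.49 next to 0.5 could take the bound as proof that the margin lies inside the established effect of individual CBT, when on that reading it does not.

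Both arms receive active CBT, so any statement about benefit over no treatment would have to come from the cited external effects. If the margin uses up the whole conservative effect, a finding of non-inferiority might be reported as if that benefit had been retained. The SAP names no fraction to be preserved and does not remark that its margin exceeds the bound it cites.

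**Working it through.** **Inputs from the SAP (Primary analysis).** Margin 0.50 SD; pooled g = 0.67 with 95% CI 0.49 to 0.85; similar-intervention trials d = 0.90 to 1.34; one-sided alpha 0.025; assumed true difference 0.

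**Assumption.** The SAP refers to the registry for sample size, so the arm sizes are assumed: 30, 63, 85 and 150. Of these, 63 and 85 per arm give about 80% and 90% power for a 0.5 SD margin at a true difference of 0. Clustering, attrition and baseline adjustment are ignored.

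**1. The cited interval is consistent.** Midpoint (0.49 + 0.85)/2 = 0.67. SE = (0.85 - 0.49)/3.92 = 0.0918. Lower bound 0.67 - 1.96 × 0.0918 = 0.49.

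**2. Fixed-margin reading.** Effect left = reference - 0.50; fraction = effect left / reference.

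| Reference | Left (SD) | Fraction |
|---|---|---|
| 0.49 (lower bound) | -0.01 | none (-2%) |
| 0.67 (pooled estimate) | 0.17 | 25% |
| 0.90 (similar trials, low) | 0.40 | 44% |
| 1.34 (similar trials, high) | 0.84 | 63% |

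Rounding does not rescue the bound: 0.485 to 0.495 leaves -0.015 to -0.005.

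**3. How often the 0.01 matters.** With SE = sqrt(2/n) and lower bound L, P(L > -m) at true difference 0 is Phi(m/SE - 1.96).

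- n = 63 (SE 0.178): 0.801 for m = 0.50 and 0.785 for m = 0.49; difference 0.016.
- n = 85 (SE 0.153): 0.903 and 0.891; difference 0.012.

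**4. Synthesis reading of a result that only just passes.** Then d = -0.5 + 1.96 × SE. The indirect effect of group treatment is 0.67 + d, with 95% limits ± 1.96 × sqrt(SE² + 0.0918²).

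| n per arm | Indirect effect | 95% CI |
|---|---|---|
| 30 | 0.676 | 0.139 to 1.213 |
| 63 | 0.519 | 0.126 to 0.912 |
| 85 | 0.471 | 0.120 to 0.821 |
| 150 | 0.396 | 0.107 to 0.685 |

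Setting the lower limit to zero gives SE = 0.0053, or n = 2/SE², about 72,000 per arm. At any feasible size the limit stays above zero.

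**5. What the plan claims.** The Aims section limits the study to how the two formats compare. The Primary hypothesis and Inferential analyses sections do the same. The Data presentation section commits to the CONSORT extension for non-inferiority trials. No section claims benefit over no treatment or a retained share of effect.

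**The case for a change.** The strongest case for a change is that the plan should say which role 0.49 plays. If judgment is the basis, the bound is context and should be labelled so. If it is support, it fails, because 0.50 exceeds it. The trials with d = 0.90 to 1.34 do not fill the gap: they are point effects without intervals, against mixed comparators. Rewording costs no patients and no alpha. The lower bound is already planned, since the lower limit of the 95% CI in Table 2 is the one-sided 97.5% bound. It could therefore be reported as 0.49 + L, the effect conservatively retained. The SAP states that "This analysis plan was constructed during data collection before data access", so a change could be made on the same terms or declared as later.

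Of this, the comparison 0.50 > 0.49 stands, as does the point that the bound taken alone does not support the margin. The rest does not carry a change. The SAP states its basis first and plainly, and the inference it draws from the cited effects is about how well individual treatment works. A disclaimer would guard against a claim that the plan never makes.

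Reporting 0.49 + L would be a doubtful addition. It adds a Hedges' g bound to a Cohen's d whose standardising SD is not specified. It assumes that the pooled effect carries over to this population, comparator and 6-month time point, which the SAP cannot show. It would also make an anchor of the very figure that the objection wants removed as support.

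**Conclusion.** No change is needed. The observation is correct but is at most a minor point of wording: the margin exceeds the cited lower bound by 0.01 SD, and on a fixed-margin reading that bound gives it no support. The margin was not derived that way. It rests on clinical judgment and the half-SD convention, and the loss it accepts is declared. Passing the test means that group CBTgrief is not worse than individual CBTgrief by 0.5 SD or more at 6 months, and readers can see this from the plan as it stands.

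The consequence is small. There is a 1.2% to 1.6% chance of a bound falling in the disputed 0.01 SD, and the indirect effect stays above zero for any result that passes at a feasible size. The probabilities rest on assumed arms of 63 and 85, a true difference of 0 and the simple standard error. The synthesis figures also assume that the pooled effect applies to this trial. The comparison of 0.50 with 0.49 needs none of these assumptions. No rewording would alter the margin, the test, the alpha or the pass/fail result.
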